#### At enrolment

Date of enrolment

Influenza A or B

Treatment with oseltamivir or zanamivir

SOFA-score the day of enrolment

Use of vasopressor

Use of continuous renal replacement therapy

Use of invasive ventilation

Use of non-invasive ventilation  
Body temperature above 38.0 degrees Celsius in the last 24 hours  
ARDS grade (defined by PaO2/FiO2 300-200 mmHg mild, 200-100 mmHg moderate, <100 mmHg severe) Treatment with corticosteroids  
Presence of haemoptysis  
Presence of pleural pain  
Ongoing treatment with antibiotics  
Ongoing treatment with antifungals

#### **Daily registration after enrolment**

SOFA-score  
Use of vasopressor  
Use of continuous renal replacement therapy  
Use of invasive ventilation  
Use of non-invasive ventilation  
Body temperature above 38.0 degrees Celsius in the last 24 hours ARDS grade (defined by PaO2/FiO2 300-200 mmHg = mild, 200-100 mmHg = moderate, <100 mmHg = severe)  
Treatment with corticosteroids  
Presence of haemoptysis  
Presence of pleural pain  
Ongoing treatment with antibiotics  
Ongoing treatment with antifungals

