### **7.3 Inclusion criteria**

Patients must meet all the inclusion criteria to be eligible for the study:  $\geq 18$  years of age, PCR-verified influenza A or B diagnosed within 7 days of ICU admission, or during ICU stay.

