## 8. WORKFLOW: OVERVIEW

## 9. DATA COLLECTION

All patient responsible physicians in the participating ICUs will be eligible to enrol patients in the study. All participating ICUs will receive both written and oral instructions about the study from the study site investigator. Data will be obtained from the participant's medical records and initially entered on a paper CRF. The empty CRF will be made available by sending prepared folders to the study sites. Additional CRFs will be made available for print from study website ([piraiastudy.se](http://piraiastudy.se)). Study site investigators will then enter the collected data into a web-based eCRF. The procedure will ensure continuous monitoring of the collected data.

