### 9.1 Data to be collected Baseline

#### characteristics

Date of ICU admission

Age

Sex

SAPS3-score on arrival to the ICU SOFA-

score on arrival to the ICU Presence of:

Liver cirrhosis (defined as Child-Pugh-score  $\geq$ A)

Heart failure (defined as ejection fraction  $<$ 40%)

Diabetes mellitus (not diet treated)

Renal failure (defined as creatinine clearance  $<$ 30 mL/min/1.73m^2)

Body Mass Index  $>$ 30 kg/m^2

Haematological malignancy

Hematopoietic stem cell transplantation

Organ transplantation

Daily smoking in the last year

Solid tumour

Neutropenia (defined as  $<$ 0,5 x10^9 neutrophils)

Chronic obstructive pulmonary disease

New lung infiltrate

Treatment with corticosteroids in the last 28 days

Treatment with corticosteroids in a dose equal to or above 15 mg/day prednisone

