## **11 STUDY ENDPOINTS**

Enrolled patients will be categorized as proven or probable IPA at discharge from the ICU to answer the primary objective of evaluating the prevalence of influenza related invasive pulmonary aspergillosis. A modified version of the Asp-ICU criteria will be used, described below 11.1, 11.2.

All recorded baseline characteristics will be compared between patients diagnosed with IPA and those that were not. The following outcome parameters will also be assessed: SOFA-score, use of mechanical ventilation, use of non-invasive ventilation, use of vasopressor, use of renal replacement therapy, ARDS-grade using the Berlin definition, median number of ICU stay, ICU mortality, and 90-day mortality after ICU admission.

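### Organ support and ARDS grade are recorded only from the day of enrolment, so ICU days before a late enrolment are absent from section 11 outcomes that have no stated time window

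*Combined protocol and SAP*

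**What the plan says.** Section 9.1 of the combined protocol and SAP collects data at four points.

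- **Baseline.** "Date of ICU admission", SAPS3 and SOFA on arrival, comorbidities, new lung infiltrate, and corticosteroids in the preceding 28 days. Organ support and ARDS grade are not listed.
- **Enrolment.** "Date of enrolment", "SOFA-score the day of enrolment", vasopressor, continuous renal replacement therapy (CRRT), invasive and non-invasive ventilation (NIV), ARDS grade, fever and current treatments.
- **Later days.** Almost the same list, under "Daily registration after enrolment".
- **ICU discharge.** Discharge date and destination, systemic antifungals over the ICU stay, and microbiology. A later record review covers microbiology and survival to 90 days from ICU admission.

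Eligibility in section 7.3 is "PCR-verified influenza A or B diagnosed within 7 days of ICU admission, or during ICU stay". Section 7.6 leaves influenza testing to clinical suspicion.

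Section 11 names as outcomes "SOFA-score, use of mechanical ventilation, use of non-invasive ventilation, use of vasopressor, use of renal replacement therapy", followed by ARDS grade, ICU stay, ICU mortality and 90-day mortality. It gives no time window for SOFA, organ support or ARDS grade. Section 6.2 also uses the need for invasive ventilation and for CRRT in the search for risk factors.

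On the source, section 9 says: "Data will be obtained from the participant's medical records and initially entered on a paper CRF".

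**The concern.** Admission and enrolment are separate dates in the plan, and SOFA is scored at each, so the plan itself allows them to differ. When they do, the days between have no field for organ support or ARDS grade.

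Take a patient who is ventilated and on vasopressors on ICU days 1 to 4, is weaned, and is enrolled on day 5. With the items as listed, that patient enters the analysis as never ventilated and never on vasopressors. A patient still supported at enrolment is counted as supported, but with too short a duration and possibly a worst value that is too mild.

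The secondary objective is at stake. The comparison of patients with and without IPA would place organ support counted from enrolment beside ICU stay and mortality counted from admission, without saying so. The early days are also those most likely to precede IPA, and they matter most if organ support is examined as a risk factor.

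**Working it through.** **1. Which items cover the days from ICU admission to enrolment?**

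| Item | On arrival | Between arrival and enrolment | Enrolment day and daily after | Whole-stay item |
|---|---|---|---|---|
| Vasopressor, CRRT, ventilation, NIV | no | no | yes | no |
| ARDS grade | no | no | yes | no |
| SOFA | yes | no | yes | no |
| Corticosteroids | preceding 28 days | no | yes | no |
| Systemic antifungals | no | no | yes | yes, at discharge |
| ICU stay, ICU and 90-day mortality | not applicable | not applicable | not applicable | yes, from dates and record review |

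The first two rows are the gap. The record review after discharge does not fill it, because it is limited to microbiology and survival.

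**2. How many patients stand behind the comparison?** The plan's own figure comes first. Section 7.2 gives an expected prevalence of 15%, a margin of 10 points and 95% confidence:

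n = 1.96² × 0.15 × 0.85 / 0.10² = 48.98, rounded up to 49.

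This agrees with the stated minimum of 50, and the present point does not alter it. At 50 patients the expected number with IPA is 50 × 0.15 = 7.5, so 7 or 8. One IPA patient wrongly recorded as unsupported moves that group's proportion by 1/8 = 12.5 to 1/7 = 14.3 percentage points.

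**3. How large could the loss be?** The documents give no enrolment delay, length of stay or duration of support. All three are assumptions here, shown over a range.

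- Share of ICU days without daily records = d / L, for delay d and stay L.
- Share of supported patients already off support at enrolment = 1 − exp(−d / m), for exponential durations with mean m. Support is taken to start at admission and not to restart.

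| Delay d (days) | Days lost, L = 5 | L = 10 | L = 20 | Off support, m = 8 | m = 12 |
|---|---|---|---|---|---|
| 0 | 0% | 0% | 0% | 0% | 0% |
| 1 | 20% | 10% | 5% | 12% | 8% |
| 2 | 40% | 20% | 10% | 22% | 15% |
| 4 | 80% | 40% | 20% | 39% | 28% |

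For example, 1 − exp(−2/8) = 1 − 0.779 = 22%.

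The last two columns apply to supported patients with that delay, not to the cohort. The cohort figure is this share times the fraction of supported patients enrolled with that delay, which the documents do not give.

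**The case against.** The strongest reply is that late enrolment may be rare. Influenza diagnosed up to 7 days before ICU admission makes a patient eligible on the first day, and consent is waived (section 7.7), so consent adds no delay. Both dates are recorded, so any lag can be reported. Starting daily follow-up at enrolment is a common prospective design. The CRF is not part of the document, and section 8 shows only a heading in the available text, so either could contain a request for earlier days. All of this stands and limits the size of the point. It does not remove the gap in section 9.1 as written, since diagnosis during the stay is expressly allowed and no maximum delay is set.

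Four stronger readings are tempting, and the documents do not support them.

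- **Section 11 promises whole-stay organ support.** A reader might infer this from the neighbouring outcomes. The section gives no window for these items. The defect is an undefined window together with collection that starts late.
- **Nothing is known before enrolment.** SOFA on arrival, corticosteroids in the preceding 28 days and systemic antifungals over the ICU stay are collected.
- **IPA status, and so prevalence, is biased.** The two fever criteria in section 11.2 do need runs of days that may precede enrolment. But any one of five clinical signs suffices, classification is made at ICU discharge, and the data come from medical records. No changed classification can be shown.
- **The loss differs between the groups.** Late diagnosis and late enrolment could both relate to a longer or more closely investigated stay, but nothing in the plan shows that they do.

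**Conclusion.** The point holds in a limited form. For patients enrolled after the admission day, section 9.1 requests no organ support or ARDS grade for the days before enrolment. Section 11 then uses these items without a window. Support that ended before enrolment is recorded as absent, and durations and worst values are left-truncated.

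The 8% to 39% range rests wholly on the assumed delays, durations and exponential shape, and it describes only supported patients with a delay of 1 to 4 days. How many patients would be enrolled late is unknown, as is the direction of any effect on the comparison of patients with and without IPA. ICU stay, ICU mortality, 90-day mortality and the sample size are untouched. The change is worth making because it is cheap and because, with 7 or 8 expected IPA patients, even one misrecorded case is visible in the results.

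**What to change.** In section 9.1 and on the CRF, register vasopressor, CRRT, invasive and non-invasive ventilation, ARDS grade and, where available, SOFA for each day from ICU admission to ICU discharge. Days before enrolment are filled from the medical record. In section 11, state that these outcomes are summarised over that same window for every patient.

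Stating a window that starts at enrolment would remove the ambiguity but would still lose the early days. Stating a whole-stay window without changing the collection would leave it without data.

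The cost is a change of CRF wording and a few more chart days per late-enrolled patient. The records are already the data source, so no new sampling or staff is needed. The downside is that SOFA scored retrospectively may have more missing components.

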#### **At discharge from the ICU**

Date of discharge from the ICU  
Discharge to (home, ward, other ICU or death)  
Treatment with systemic antifungals during the care time in the ICU  
Microbiological findings: Positive Aspergillus culture or microscopy, GM in BAL or serum or Beta-D-Glucan.

#### **Medical records**

Medical records will be reviewed for information on microbiological findings and survival up to 90 days from ICU admission.

## **9.2 Confidentiality**

Study participants will be assigned a unique study identification number (e.g., LU01 - first patient in Lund). CRF will be pseudo-anonymized using the identification number. Each study site will receive a "code list" where the personal number of the study participant will be linked to the study identification number. Study site investigators are responsible for keeping the "code list" separated from the CRFs. The

study site investigators will continuously transfer the information to the eCRF to ensure the security of the data.

### **9.3 Access to data**

All CRFs will be archived for 15 years. De-identified data (individual data that underlie the results reported in the study) will be made available beginning 3 months and ending 5 years after the publication of the study.

## **10 QUALITY ASSURANCE AND QUALITY CONTROL**

The principal investigator will be responsible for organizing the study sites including education of study site investigators. Study folders will be prepared for the study investigators, including outlines of the data collection process, study protocol and CRF. After initiation of the study, the study site investigators will be responsible for all study-related procedures at their site.

Using the eCRF, data collection will be continuously and closely monitored. The principal investigator will issue queries about missing data, out of range values, or illogical data relations.

## **11 STUDY ENDPOINTS**

Enrolled patients will be categorized as proven or probable IPA at discharge from the ICU to answer the primary objective of evaluating the prevalence of influenza related invasive pulmonary aspergillosis. A modified version of the Asp-ICU criteria will be used, described below 11.1, 11.2.

All recorded baseline characteristics will be compared between patients diagnosed with IPA and those that were not. The following outcome parameters will also be assessed: SOFA-score, use of mechanical ventilation, use of non-invasive ventilation, use of vasopressor, use of renal replacement therapy, ARDS-grade using the Berlin definition, median number of ICU stay, ICU mortality, and 90-day mortality after ICU admission.

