### **6.2 Secondary objective**

To assess the clinical impact and risk factors related to influenza-related invasive pulmonary aspergillosis. Patients with proven or probable IPA will be compared to patients that do not meet the criteria for proven and probable IPA. Baseline characteristics and clinical data such as SAPS3, SOFA score, need for invasive ventilation and need for continuous renal replacement therapy, will be assessed to find risk factors for IPA.

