### **11.1 Proven invasive pulmonary aspergillosis**

Microscopic analysis on sterile material: histopathologic, cytopathologic, or direct microscopic examination of a specimen obtained by needle aspiration or sterile biopsy in which hyphae are seen accompanied by evidence of associated tissue damage. Culture on sterile material: recovery of *Aspergillus* by culture of a specimen obtained by lung biopsy.

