### **11.2 Probable invasive pulmonary aspergillosis (fulfil both clinical, radiological and mycological criteria)**

**Clinical criteria:** One of the following signs or symptoms must be present:

- Fever refractory to at least 3 days of appropriate antibiotic therapy.
- Recrudescence fever after a period of defervescence of at least 48 h while still on antibiotics and without other apparent cause
- Dyspnea
- Hemoptysis
- Pleural friction rubs or chest pain

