**Radiological criteria:**

Any infiltrate on pulmonary imaging by portable chest x-ray or CT-scan of the lungs.

**Mycological criteria:** One of the following findings:

- Positive microscopy or culture of *Aspergillus* from BAL
- Galactomannan optical index on BAL >0,8
- Galactomannan optical index on serum  $\geq 0,5$

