## **12 STATISTICAL ANALYSIS**

Prevalence of Proven/Probable IPA will be calculated at the 95% confidence level. Patients meeting the criteria for proven/probable IPA will be compared to the influenza positive patients who do not meet the criteria, in terms of underlying risk factors and outcome measures. Categorical variables will be assessed by Fischer exact test and  $X^2$  test, and continuous variables with t-test or Mann Whitney U test where appropriate. We will also perform multivariable analysis by binary logistic regression to detect independent risk factors for IPA. All analyses will be conducted using a threshold of 95% confidence level (P-value 0.05). ICU mortality and 90 days after admission to the ICU mortality will be compared using survival analysis.

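### New lung infiltrate is compared as a candidate risk factor for IPA, although an infiltrate is required for probable IPA, so part of any association is built in by the definition

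*Combined protocol and SAP*

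**What the plan says.** - **Variable.** Section 9.1 lists "New lung infiltrate" among the baseline characteristics.
- **Comparison.** Section 11 makes no exception: "All recorded baseline characteristics will be compared between patients diagnosed with IPA and those that were not".
- **Purpose.** Section 6.2 says baseline and clinical data "will be assessed to find risk factors for IPA". Section 12 adds: "We will also perform multivariable analysis by binary logistic regression to detect independent risk factors for IPA". It does not list the covariates.
- **Outcome.** Section 11.2 makes probable IPA conjunctive ("fulfil both clinical, radiological and mycological criteria"). The radiological criterion is "Any infiltrate on pulmonary imaging by portable chest x-ray or CT-scan of the lungs". Proven IPA (section 11.1) has no imaging requirement.
- **Timing.** Section 11: "Enrolled patients will be categorized as proven or probable IPA at discharge from the ICU".
- **Comparator.** Section 12 uses the influenza-positive patients who do not satisfy the proven/probable criteria.

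Nothing in the document exempts the infiltrate variable from the comparison or warns of the overlap.

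**The concern.** A candidate predictor overlaps a necessary condition of the outcome (incorporation bias). Take two patients with the same positive galactomannan and the same dyspnoea. The one with an infiltrate is a case. The one who never shows an infiltrate is a non-case, unless IPA is proven. The definition therefore enriches cases for infiltrate and depletes the comparator of it, whatever the biology.

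Risk factors are the secondary objective, and section 5.2 looks ahead to national testing guidelines. A report that infiltrate predicts IPA could be read as a reason to test patients with infiltrates first, when some or all of the association comes from the case definition.

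**Working it through.** **The plan's own figure.** Section 7.2 gives 50 patients for an expected prevalence of 15% and a 10% margin of error at 95% confidence. n = 1.96² × 0.15 × 0.85 / 0.10² = 48.98, so 49. The stated 50 is reproduced, with a half-width of 9.9 percentage points at n = 50. The sample size is sound.

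**Inputs from the documents.** IPA 15%; n = 50 (minimum) and about 100 (patients per season at the participating centres), all from section 7.2; threshold 0.05 from section 12, taken as two-sided.

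**Inputs assumed, because the documents give none.**
- *b*: share of patients with a new infiltrate at baseline, 60% to 80%, with 90% as a check.
- *f*: share of the remaining patients who show any infiltrate by ICU discharge, 0 to 1.
- All cases are probable, none proven.

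**Null model.** Infiltrate has no effect. The clinical and mycological criteria are jointly met with probability *q*, regardless of infiltrate. Then:
- P(IPA | baseline infiltrate) = *q*
- P(IPA | no baseline infiltrate) = *q f*
- built-in risk ratio = *q* / (*q f*) = 1/*f*
- *q* = 0.15 / (*b* + (1 − *b*) *f*), which fixes total IPA at 15%

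**Worked case, b = 0.6, f = 0.25.** *q* = 0.15 / (0.6 + 0.4 × 0.25) = 0.214 and *q f* = 0.054. Odds ratio = (0.214/0.786) / (0.054/0.946) = 4.8. Baseline infiltrate is then present in 0.6 × 0.214 / 0.15 = 86% of cases and 0.6 × 0.786 / 0.85 = 55% of non-cases, with no true effect.

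**Worked case, b = 0.6, f = 0.5.** *q* = 0.15 / 0.8 = 0.1875 and *q f* = 0.094. Odds ratio = 0.231 / 0.103 = 2.2.

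**Rejection rate** of the two-sided Fisher test at 0.05, by exact enumeration, with the number of patients with a baseline infiltrate treated as binomial:

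| f | Built-in odds ratio (b = 60–80%) | n = 50, b = 60 / 70 / 80% | n = 100, b = 60 / 70 / 80% |
|---|---|---|---|
| 0 | infinite | 68 / 34 / 6% | >99 / 93 / 49% |
| 0.25 | 4.8 to 4.6 | 23 / 12 / 2% | 57 / 39 / 17% |
| 0.5 | 2.2 | 8 / 4.5 / 1% | 19 / 13 / 6% |
| 0.75 | 1.4 | 3 / 2 / 1% | 6 / 4 / 3% |
| 1 | 1.0 | 2 to 3% | 3 to 4% |

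The last row is the reference: without the built-in effect, this conservative test rejects in 2% to 4%. At *b* = 90% and *f* from 0 to 0.75, rejection is about 1% or less at either sample size, although the odds ratio is still 1.4 or more.

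**The case against.** **The variable and the criterion are not the same thing.** The baseline item is a new infiltrate. The criterion is any infiltrate, judged at ICU discharge, and proven IPA needs none. This stands. A patient without a new infiltrate at baseline can still become a case, so a reader who infers that infiltrate must be present at baseline in every case, or that a significant result is guaranteed, goes beyond the text. The *f* = 0 row is an extreme case, not the plan as written. But the bias vanishes only if *f* = 1 or if essentially all cases are proven. The routine in section 3 consists of serum markers and weekly respiratory samples, so few cases are likely to meet the tissue or sterile-specimen definition in section 11.1.

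**Significance may be rare.** This also stands. At n = 50, many combinations in the table reject at or below 5%. The odds ratio is biased all the same, and it would be reported.

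**The symptoms.** A reader might extend the point to haemoptysis, pleural pain and fever. The documents do not support that as the same circularity. Section 9.1 records these at enrolment and daily, not among the baseline characteristics that section 11 compares. Each is only one of five alternative signs in section 11.2, with dyspnoea among them. The recorded fever item (above 38.0 °C in the last 24 hours) is also not the fever criterion, which is refractory or recrudescent fever under antibiotics.

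**The logistic model.** A reader might infer that the regression will break down. Section 12 names no covariates, so inclusion of the infiltrate is possible but not stated. An infinite coefficient also needs an empty cell. This harm is conditional.

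**Comparing by mycological result instead.** This is not a clean substitute. The plan defines no such outcome, and section 7.1 leaves sampling to the physician, whose decision may itself depend on an infiltrate.

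**Conclusion.** The point holds for new lung infiltrate alone. Read together, sections 9.1, 11, 11.2 and 12 commit the plan to a comparison whose result is partly fixed by the case definition. With no true effect, the built-in risk ratio is 1/*f*. For *f* between 0.25 and 0.5, that means an odds ratio of about 2.2 to 4.8. The false-positive rate then ranges from 1% to 23% at n = 50 and from 6% to 57% at n = 100, for baseline infiltrate in 60% to 80%.

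These figures rest on assumed values of *b* and *f* and on all cases being probable; proven cases would dilute the effect. The existence and direction of the bias do not depend on the particular values, short of *f* = 1 or nearly all cases proven. The size does. The point is minor: one baseline variable in a secondary analysis, with no effect on the primary prevalence estimate or the sample size.

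**What to change.** Add one sentence to sections 11 and 12: new lung infiltrate is described by group, but because an infiltrate is part of the probable-IPA definition, it is not tested or interpreted as a risk factor for IPA and does not enter the logistic model.

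This needs no new data and leaves the target of 50 patients and the prevalence analysis as they are. The only loss is one comparison that could not have been interpreted.
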